Appendix 7. Blood Sampling Summary

This table summarizes the approximate number of samples and blood volumes for all blood sampling (screening, safety laboratories, bioanalytical assays, and the other tests) during the study.

Protocol I8F-JE-GPGC Sampling Summary

Purpose	Blood Volume per Sample (mL)	Number of Blood Samples		Total Volume (mL)	
		Cohort 1 or 2	Cohort 3	Cohort 1 or 2	Cohort 3
Screening serology and Serum pregnancy tests ^a	9 ^b	1	1	9	9
Clinical safety laboratory tests ^a	10 ^b	20	16	200	160
Lipid panel	2.5	3	3	7.5	7.5
LY3298176 pharmacokinetics	3	18	18	54	54
Potential additional LY3298176 pharmacokinetic samples	3	3	3	9	9
Glucagon	2	15	13	30	26
Fasting plasma glucose and insulin	4.5	15	13	67.5	58.5
Oral glucose tolerance test (serum glucose and insulin)	2.5	10	10	25	25
HbA1c	2	4	4	8	8
Immunogenicity	6	4	4	24	24
Exploratory storage sample ^d					
Adiponectin	2	2	2	4	4
Cortisol	2.5	3	3	7.5	7.5
Bone biomarkers	3.5	2	2	7	7
Pharmacogenetics	6	1	1	6	6
Nonpharmacogenetics Storage sample	4.5	6	6	27	27
Total				485.5 ^c	432.5 ^c

Abbreviation: HbA1c = hemoglobin A1c.

^a Additional samples may be drawn if needed for safety purposes.

^b Because screening and safety (chemistry and hematology) tests are performed at local laboratories at each site, this volume is an estimate and will vary depending on the local laboratory's testing requirements.

^c The maximum blood volume will increase if follow-up visits for antidrug antibody testing are needed.

^d Blood volumes for this storage sample is calculated based on the assumption that the following biomarkers will be assayed for.

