9.4.2 Pharmacodynamic Statistical Methodology

Statistical inference on PD parameters (fasting blood glucose, OGTT glucose, and insulin) will be based on the patients who are included in the PD population. PD parameters may be transformed before statistical analyses, if deemed necessary.

The observed results, as well as change from baseline, will be analyzed by treatment regimen, using mixed-effects models to evaluate treatment effects, as well as treatment comparisons. The model will include treatment regimen actually received, as a fixed effect and the patient as a random effect. For repeated measured parameters, day and treatment regimen-by-day interaction terms will be included in the model. Baseline (Day -1) values, as well as other influencing variables, may be used as covariates. An unstructured covariance structure will be applied. If the model fails to converge, alternative structures shall be examined using Akaike's criteria. The main comparisons will be between each LY3298176-treated group and placebo group. Least-squares means as well as 95% CIs will be reported.

Example SAS code for repeated measures analysis:

```
proc mixed data=pd;
  class subject trtreg day;
  model chg = base trtreg day trtreg*day / residual ddfm=kr;
  repeated day / subject=subject type=un;
  lsmeans trtreg / alpha=0.05 cl pdiff;
  ods output lsmeans=lsm;
  ods output diffs=diff;
run;
```

where 'chg' is the change from baseline, 'base' is the baseline value, and 'trtreg' is the treatment regimen.

Example SAS code for mixed-effects analysis:

```
proc mixed data=pd;
  class subject trtreg;
  model pd = trtreg / residual ddfm=kr;
  random subject;
  lsmeans trtreg / alpha=0.05 cl pdiff;
  ods output lsmeans=lsm;
  ods output diffs=diff;
run;
```

where 'trtreg' is the treatment regimen.

The individual observed and mean (SD) time profile of the postdose PD parameters will be plotted by treatment regimen. Additional exploratory analyses of PD parameters may be performed to understand dose response using relevant model considering titration scheme, as deemed appropriate.

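### The OGTT analysis does not require the Day -1 OGTT as a covariate: the example program that fits it omits baseline and carries an unidentifiable patient effect, and SAP 9.4.1 names a baseline day with no OGTT

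*SAP*

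**What the plan says.** SAP 9.4.2 lists what will be tested: "Statistical inference on PD parameters (fasting blood glucose, OGTT glucose, and insulin) will be based on the patients" in the PD population. It states that "The observed results, as well as change from baseline, will be analyzed by treatment regimen, using mixed-effects models", and that "The model will include treatment regimen actually received, as a fixed effect and the patient as a random effect". On baseline it says "Baseline (Day -1) values, as well as other influencing variables, may be used as covariates".

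Two example programs follow. The repeated-measures program is "model chg = base trtreg day trtreg*day / residual ddfm=kr". The second is "model pd = trtreg / residual ddfm=kr" with "random subject"; it has no baseline term and no day term, and the SAP does not define its response variable or tie the program to a named endpoint.

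SAP 9.4.1 says that OGTT AUC(0-2h) and the timepoint values will also be baseline-adjusted, but takes the baseline from Day 1 predose. Protocol 10.3.3.1 takes it from Day -1. Protocol 9.6.1.2 places the baseline OGTT on Day -1, and the schedules show none on Day 1. SAP section 3 says the SAP supersedes the protocol's statistical considerations; SAP section 11 reports no changes.

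Protocol 9.6.1.1 gives five samples per OGTT. The row "Oral glucose tolerance test (serum glucose and insulin") in Appendix 7 allots ten per patient.

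**The concern.** A baseline OGTT is collected from every patient, yet the program that fits the OGTT does not use it. If that program were run as written on observed values, chance differences in baseline glucose tolerance between small arms would pass into the treatment contrast. The change-from-baseline analysis uses the Day -1 test but, without the covariate, over-corrects for it. Whether to adjust is left open until the data are in hand.

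Two further faults sit in the same place. A patient random effect has no meaning with one record per patient. And the SAP's baseline day, read literally, leaves no baseline AUC(0-2h) to adjust for. At stake are the width of the OGTT intervals and a clear, pre-specified estimate.

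**Working it through.** **1. Which program applies.** Ten samples at five per test is two OGTTs: one on Day -1 and one later. The day column of the later test is unclear in the extracted schedules, so the count rests on Appendix 7. One post-baseline occasion does not suit a program with day and regimen-by-day terms, which leaves the second.

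**2. Arm sizes.** The plan states no precision for the OGTT; its only sizing figures are about 49 enrolled and about 32 completing (SAP section 7).
- Enrolled: 15 + 19 + 15 = 49, as stated.
- Completers: 15×0.7 + 19×0.5 + 15×0.7 = 30.5, close to 32.
- Active arms are 12, 16 and 12 against 9 pooled placebo. Expected completers are 8.4, 8.0 and 8.4 against 3×0.7 + 3×0.5 + 3×0.7 = 5.7, so about 8 v 6.

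**3. The random effect.** With one record per patient, only the sum of the patient and residual variances enters the likelihood. For a simulated set of 49 patients (arms 9/12/16/12), the REML log-likelihood was -22.48551 with the patient share of variance at 0, 25, 50, 75 and 99%. The treatment difference and its standard error were also the same at every split. The fit is a one-way ANOVA with a redundant term.

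**4. Chance baseline imbalance**, in between-patient SD units:
- 12 v 9: √(1/12 + 1/9) = 0.44
- 16 v 9: √(1/16 + 1/9) = 0.42
- 8 v 6: √(1/8 + 1/6) = 0.54

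Under normality it exceeds 0.5 SD with probability 0.26 (12 v 9) or 0.36 (8 v 6).

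**5. What each contrast carries.** Let ρ be the correlation of the baseline and later OGTT values, with equal variances. The observed-value contrast carries ρ times the imbalance, the unadjusted change contrast -(1-ρ) times it, and ANCOVA about none. In 20,000 simulated trials (arms 9/12/16/12) at ρ = 0.5, 0.7 and 0.8, the slopes on imbalance were:
- observed value: 0.51, 0.70, 0.79
- change: -0.49, -0.31, -0.21
- ANCOVA: 0.01, -0.01, -0.01

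All three estimators averaged within 0.005 SD of the true value. At ρ = 0.7 and 12 v 9, the SD of the part carried is 0.7×0.441 = 0.31 for the observed value and 0.3×0.441 = 0.13 for change.

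**6. Standard errors, 12 v 9.** With k = √(1/12 + 1/9) = 0.441:
- observed value: k
- change: k√(2(1-ρ))
- ANCOVA: k√(1-ρ²)·√(1 + 1/43), where 43 = 49 - 4 - 2; the last factor is the cost of estimating the slope

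| ρ (assumed) | Observed | Change | ANCOVA | ANCOVA v change | ANCOVA v observed |
|---|---|---|---|---|---|
| 0.3 | 0.441 | 0.522 | 0.426 | 18% lower | 3.5% lower |
| 0.5 | 0.441 | 0.441 | 0.386 | 12% lower | 12% lower |
| 0.7 | 0.441 | 0.342 | 0.319 | 7% lower | 28% lower |
| 0.8 | 0.441 | 0.279 | 0.268 | 4% lower | 39% lower |
| 0.9 | 0.441 | 0.197 | 0.194 | 1–2% lower | 56% lower |

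For 8 v 6 completers (N = 30) at ρ = 0.5, 0.7 and 0.8, the errors are 0.540 for the observed value; 0.540, 0.418 and 0.342 for change; and 0.477, 0.394 and 0.331 for ANCOVA.

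**The case against.** A reader might infer that the Day -1 OGTT is thrown away. The documents do not support that. The section commits to a change-from-baseline analysis, which cannot be computed without a baseline test; it permits the Day -1 covariate; and 9.4.1 promises baseline adjustment. The programs are labelled examples, and the undefined response could hold a change value. Because the change score is already planned, the fair comparator is that score, and the gain over it is smallest where the gain over the observed-value model is largest.

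A reader might also infer that the random effect distorts the result. It does not: the estimate and model standard error are unchanged. Convergence or Kenward-Roger degrees-of-freedom trouble is possible but has not been shown.

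Nor is the imbalance a bias on average over randomization; it affects precision and the estimate conditional on the imbalance that occurs.

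Finally, the OGTT is exploratory and the study sets no statistical requirement for its size. The secondary PD endpoint, fasting glucose, is measured repeatedly and falls under the program that does include baseline.

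All of this stands, and it limits the point. It does not remove it. No reading makes the second program suitable for the OGTT. With a change score as response, the covariate is still missing and the random effect still unidentifiable. With both tests stacked, the random effect becomes identifiable, but without a day term the contrast averages pre- and post-treatment values and, with complete pairs, halves the expected effect. And the baseline adjustment in 9.4.1 points to a day without an OGTT.

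**Conclusion.** The concern holds as a matter of specification and precision. The Day -1 OGTT is used in the planned change score but is not required as a covariate, the random patient term is redundant, and the OGTT baseline day in SAP 9.4.1 contradicts both SAP 9.4.2 and protocol 10.3.3.1. Requiring the covariate lowers the standard error by about 12%, 7% and 4% against the planned change score at correlations of 0.5, 0.7 and 0.8, and by about 12%, 28% and 39% against the observed-value model.

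These figures assume equal baseline and post-treatment variances and a correlation that the documents do not give. That the second program is meant for the OGTT is an inference by elimination, though a firm one. The change is worth making because it is cheap and settles an analysis choice in advance; no primary or secondary conclusion depends on it.

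**What to change.** For OGTT glucose and insulin, at each timepoint and for AUC(0-2h):

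- Replace the second example program with a fixed-effects ANCOVA, `model pd = base trtreg`, with no random statement, where `base` is the same quantity from the Day -1 OGTT.
- In the text of 9.4.2, make this covariate mandatory (will instead of may).
- In 9.4.1, set the OGTT baseline to Day -1. Limit the correction to the OGTT, since fasting samples are taken at Day 1 predose.
- Report the least-squares mean difference from placebo with its 95% CI once. With `base` in the model, subtracting it from the response shifts only its own coefficient, so the observed-value and change contrasts are identical.

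The cost is a few lines of SAP text and code and one degree of freedom. Patients without a Day -1 OGTT drop out of this model; their number should be stated.

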9.4.3 Pharmacokinetic/Pharmacodynamic Analyses

PK/PD modeling may be used to characterize the exposure-response relationships between LY3298176 concentrations and various PD and key safety endpoints, provided data are sufficient, and will be reported separately.

9.5 Safety and Tolerability Assessments

9.5.1 Adverse events

Where changes in severity are recorded in the Case Report Form (CRF), each separate severity of the AE will be reported in the listings, only the most severe will be used in the summary tables. A pre-existing condition is defined as an AE that starts before the patient has provided written informed consent and is ongoing at consent. A non-treatment emergent AE is defined as an AE which starts after informed consent but prior to dosing. A treatment-emergent AE (TEAE) is defined as an AE which occurs postdose or which is present prior to dosing and becomes more severe postdose. AEs will also be presented by day of onset.

All AEs will be listed. TEAEs will be summarized by treatment regimen, severity, and relationship to the study drug. The frequency (the number of AEs, the number of patients experiencing an AE and the percentage of patients experiencing an AE) of TEAEs will be summarized by treatment regimen, Medical Dictionary for Regulatory Activities (MedDRA) version 20.0 system organ class, and preferred term. The summary and frequency AE tables will be presented for all causalities and those considered related to the study drug. Any serious AEs will be tabulated.

9.5.2 Concomitant medication

Concomitant medication will be coded using the WHO drug dictionary (Version March 2017 Enhanced Dictionary B2 Format). Concomitant medication will be listed.

9.5.3 Clinical laboratory parameters

All clinical chemistry and hematology data will be summarized by treatment regimen and parameter together with changes from baseline, where baseline is defined as Day -1, and listed. Urinalysis data will be listed. Additionally clinical chemistry, hematology, and urinalysis data outside the reference ranges will be listed.

Values for any clinical chemistry, hematology, and urinalysis values outside the reference ranges will be flagged on the individual patient data listings.

9.5.4 Vital signs

Vital signs data will be summarized by treatment regimen together with changes from baseline, where baseline is defined as Day 1, predose. Figures of mean vital signs and mean changes from baseline profiles will be presented by treatment regimen. Furthermore, values for individual patients will be listed.

For change from baseline in vital signs, a mixed-model repeated-measure model with treatment regimen, time (of measurement), and treatment regimen-by-time interaction as fixed effects, patient as random effect, and baseline as covariate will be used to determine the effects of LY3298176. An unstructured covariance structure will be applied. If the model fails to converge, alternative structures shall be examined using Akaike's criteria. Least-squares means, as well as 95% CIs, will be reported.

Example SAS code:

```
proc mixed data=safety;
  class subject trtreg day;
  model chg=trtreg day trtreg*day base / residual ddfm=kr;
  repeated day / subject=subject type=un;
  lsmeans trtreg*day / alpha=0.05 cl pdiff;
  ods output lsmeans=lsmeans;
  ods output diff=diffs;
run;
```

where 'chg' is the change from baseline, 'base' is the baseline value, and 'trtreg' is the treatment regimen.

9.5.5 Electrocardiogram (ECG)

The ECG data will be obtained directly from the 12-lead ECG traces. These data include the PR, QT, QTcB intervals, QRS duration and heart rate, where QTcB is the QT interval corrected using Bazett's formula. In addition, QTcF (the QT interval corrected using Fridericia's formula) will be calculated as follows:

$$QTcF = \frac{QT}{\sqrt[3]{(60/HR)}}$$

The ECG data will be summarized by treatment regimen together with changes from baseline, where baseline is defined as the mean of all measurements on Day 1 predose of the treatment period. Figures of mean ECG data and mean changes from baseline will be presented by treatment regimen.

A plasma LY3298176 concentration-QT analysis will be performed to assess the changes from baseline (Day 1 predose) and placebo in the (double delta) QTcF interval relative to plasma LY3298176 concentrations across all active treatments. The change from baseline adjustment will be based on individual subject's Day 1 predose value, and the change from placebo adjustment will be based on the mean of time-matched placebo values.

Further details on how these will be calculated:

- Calculate the arithmetic mean of the triplicate QTcF for each subject at each timepoint and use this in all subsequent calculations below.
- Calculate the change from baseline at each timepoint for each individual subject who received LY3298176.
- Calculate the mean change from baseline across all the placebo subjects at each timepoint.

- For each subject that received LY3298176 at each corresponding timepoint subtract the mean placebo change from their own individual change from baseline.
- BLQ LY3298176 concentration data will be imputed to 50% of the LLOQ for the purposes of the analysis.

The analysis will be performed by plotting double delta QTcF against LY3298176 concentrations, including all post Day 1 dosing timepoints.

A mixed effects analysis model will be performed on the double delta QTcF values and will include LY3298176 concentration as a covariate and subject as a random effect. The results of the model and associated 90% CI will be fitted on the plot and the p-value for the slope reported. Estimated double delta QTcF and 90% CI at the geometric mean C_{max} will also be presented.

Additional analysis to evaluate effects of AE (such as gastrointestinal or hypoglycemia events) QTcF may be performed if deemed necessary.

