10.3.1.2. Statistical Evaluation of Safety

Safety parameters that will be assessed include safety laboratory parameters, vital signs, ECG parameters, injection-site reactions, and hypoglycemia. The parameters will be listed and summarized using standard descriptive statistics.

Laboratory measurements will be summarized with respect to observed values and change from baseline by treatment group at each time point using descriptive statistics. In addition, all clinical chemistry, hematology, and urinalysis data outside the reference ranges will be tabulated by parameter and treatment group.

Vital signs will be summarized with respect to observed values and change from baseline (Day 1, Predose) by treatment at each time point using descriptive statistics. For change from baseline values, a mixed-model repeated-measure model with treatment, time (of measurement), and treatment-by-time interaction as fixed effects, patient as random effect, and baseline as covariate will be used to determine the effects of LY3298176.

Electrocardiogram parameters, including the pulse rate, QT interval, RR interval, and QTc using Fridericia's formula (QTcF), QRS interval duration, and heart rate, will be summarized. The number and percentage of patients with a maximum increase from baseline in QTcF will be summarized for each treatment group according to the following categories: >30 milliseconds and >60 milliseconds. In addition, the number and percentage of patients with QTcF postdose values according to the following categories: >450 milliseconds, >480 milliseconds, and >500 milliseconds, will be summarized by treatment group. Exploratory analyses may be performed to determine the effects of LY3298176 concentration-response analysis of QTcF.

Additional analysis will be performed, if warranted, upon review of the data.

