7. SAMPLE SIZE JUSTIFICATION

The sample size for the study was chosen to provide sufficient data to evaluate the primary objective of this study and is not intended to achieve any a priori statistical requirements.

Approximately 49 Japanese patients with T2DM may be enrolled so that approximately 32 patients complete the study with compliant defined dosing regimen. The estimated drop-out rates are 30% for Cohorts 1 and 3 and 50% for Cohort 2. Patients will be administered 8 weekly SC doses of LY3298176 or placebo in a ratio of 12 LY3298176 : 3 placebo for Cohorts 1 and 3, and 16 LY3298176 : 3 placebo for Cohort 2. Considering the possibility of higher drop-out rate when administered the highest dose level of LY3298176, the number of patients to be enrolled in Cohort 2 is higher than those for the other 2 cohorts.

Replacement of discontinued patients is not planned because the sample size is determined considering the expected drop-out rate.

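### The concentration-QTc model omits the sampling error of the subtracted placebo mean (9 patients), so its 90% CI at Cmax is roughly 1.8 to 2.3 times too narrow and the slope p-value is too small

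*SAP*

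**What the plan says.** SAP 9.5.5 (Electrocardiogram) builds the analysis in steps. Triplicate QTcF values are averaged and each patient's change from the Day 1 predose value is taken. One mean change is computed over all placebo patients at each time point. Then: "For each subject that received LY3298176 at each corresponding timepoint subtract the mean placebo change from their own individual change from baseline". For the model: "A mixed effects analysis model will be performed on the double delta QTcF values and will include LY3298176 concentration as a covariate", and subject is the random effect. Placebo patients are not in this model. It has no time or treatment term, and no variance correction is described.

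On reporting: "The results of the model and associated 90% CI will be fitted on the plot and the p-value for the slope reported". The SAP also promises the estimated double-delta QTcF with a 90% CI at the geometric mean Cmax.

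Protocol 10.3.1.2 is softer: "Exploratory analyses may be performed to determine the effects of LY3298176 concentration-response analysis of QTcF". The SAP turns this into an analysis that will be done.

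The preceding section, SAP 9.5.4 (Vital signs), takes another route. It uses change from baseline and "a mixed-model repeated-measure model with treatment regimen, time (of measurement), and treatment regimen-by-time interaction as fixed effects", so placebo patients stay in the model.

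**The concern.** The placebo mean is an estimate from few patients. If it happens to be 2 ms too low at some time point, all 40 double-delta values at that time point are 2 ms too high together. A subject random effect treats the LY3298176 patients as independent of each other, so it cannot represent an error they share. The model takes the placebo mean as known.

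The interval at Cmax suffers most, because the constant part of the placebo error goes straight into the fitted level. The slope suffers too. Concentration rises with time on study through accumulation and, in Cohorts 1 and 2, titration, so errors shared within time points partly line up with concentration.

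This is the only inferential QT analysis the SAP commits to; the PK/PD modelling in SAP 9.4.3 is optional. As planned, it would overstate how precisely the QTcF effect is known. It could make an effect look better excluded than it is, or make a drug with no effect appear to have a concentration-related one.

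**Working it through.** **Inputs from the documents.** SAP 7 gives 12:3 for Cohorts 1 and 3 and "16 LY3298176 : 3 placebo for Cohort 2". That is 12 + 16 + 12 = 40 LY3298176 and 3 + 3 + 3 = 9 placebo patients, 49 in total, matching the stated enrolment. SAP 8 pools placebo. On drop-out: "The estimated drop-out rates are 30% for Cohorts 1 and 3 and 50% for Cohort 2". Expected completers are 15 × 0.7 + 19 × 0.5 + 15 × 0.7 = 30.5, or 11 + 10 + 11 = 32 if each cohort is rounded up, matching the stated figure of about 32.

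**Closed form.** Let σ² be the between-patient variance of the change, equal in both arms.

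- The model's variance for the mean double delta is σ²/40.
- The true variance is σ²/40 + σ²/9.
- The ratio of standard errors is sqrt(1 + 40/9) = sqrt(49/9) = 2.33. No value of σ is needed.

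With the planned drop-out, LY3298176 completers number 8.4 + 8 + 8.4 = 24.8. If placebo patients leave at the same rates, 2.1 + 1.5 + 2.1 = 5.7 remain and the ratio is sqrt(1 + 24.8/5.7) = 2.31. If no placebo patient leaves, it is sqrt(1 + 24.8/9) = 1.94.

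For scale, assume σ = 7 ms and count only the between-patient part. The reported half-width is 1.645 × sqrt(49/40) = 1.8 ms. The correct one is 1.645 × sqrt(49/40 + 49/9) = 4.2 ms.

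**Simulation.** The closed form covers only between-patient error, so the whole SAP procedure was simulated with no true drug effect. There were 2,000 runs per setting and 15 post-dose ECG times from Day 1 (8 h) to Day 64. Concentrations came from a one-compartment model with a 120 h half-life on the protocol's dosing schedules. The documents give no QTcF variance, so these are assumptions: between/within-patient SD 4/8, 7/7 and 10/5 ms, PK CV 30%, and residuals independent over time. The factor below is the true SE divided by the model's SE, at the Cmax of each regimen.

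| | 40:9 (planned enrolment) | about 25:9 (drop-out in LY3298176 only) |
|---|---|---|
| Closed-form factor | 2.33 | 1.94 |
| Simulated factor at Cmax | 2.08-2.36 | 1.75-1.98 |
| Coverage of nominal 90% CI | 53-58% | 60-67% |
| Slope SE factor | 1.9-2.0 | 1.6-1.7 |
| Slope p < 0.05 under no effect | 30-32% | 22-24% |

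At 40:9 the reported half-width was 1.6-3.1 ms against a correct 3.7-6.8 ms.

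**Consistency check.** A factor of 2.33 implies coverage of 2Φ(1.645/2.33) − 1 = 52%. Slope factors of 1.9 and 2.0 imply rejection of 2[1 − Φ(1.96/1.9)] = 30% and 2[1 − Φ(1.96/2.0)] = 33%. Both agree with the table.

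**Second simulation.** A separate program (300 runs per setting, SD pairs from 0.5/8 to 10/5 ms) gave a factor of 1.78-2.37 at Cmax with all 49 patients, coverage of 49-67% and slope rejection of 25-34%. The low end is the case where almost all variance is within patients. With drop-out in both arms and partial data kept, the factor was 1.8-2.8 and slope rejection 25-46%.

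**Placebo kept in the model.** A one-step model fitted to both arms gave 89-91% coverage and 4-5% slope rejection with independent residuals.

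**The case against.** The strongest reply is that little depends on this analysis. The protocol calls it exploratory, adverse events are the primary endpoint, and the sample size has no statistical target. Neither document sets a millisecond threshold or a rule for acting on the interval. QTc limits for individual patients sit in the clinically significant event table (Protocol Appendix 4) and are unaffected. All of this stands, and it limits the severity. It does not make the interval correct, and the SAP commits to reporting it.

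The SAP also sets no significance level for the slope, so the 5% used here is only a yardstick. That is fair, but a p-value that falls below 0.05 in 22-32% of null studies is miscalibrated whatever cut-off the reader applies.

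The size rests on assumed variances and drop-out patterns. That stands too, and the range of 1.8 to 2.3 is not a firm bound. The departures examined, however, mostly make matters worse. Drop-out in both arms pushed the factor as high as 2.8. An assumed 7-day residual correlation of 0.3 raised slope rejection to 47-56%.

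Finally, the vital-signs model estimates regimen effects by time, not a concentration slope. It shows that placebo can be kept in a model; it is not a contradiction within the SAP.

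**Conclusion.** The point holds. As written, SAP 9.5.5 treats a mean of 9 placebo patients as known. The 90% CI at geometric mean Cmax is too narrow by a factor of roughly 1.8 to 2.3, and the slope standard error is understated by about 1.6 to 2.0.

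The direction, and the closed-form value of 2.33 for between-patient error, follow from the planned 40:9 allocation with equal variance in the two arms. The rest of the range depends on the assumed split of QTcF variance, on who drops out, and on residuals being independent over time. The analysis is exploratory and patient protection does not rest on it, so this is something that should be fixed rather than a critical fault.

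**What to change.** Fit one model to change-from-baseline QTcF in all patients, with placebo at concentration 0. Use fixed effects for active versus placebo, nominal time, concentration and baseline QTcF, with subject as a random effect. Report the double-delta estimate and 90% CI at geometric mean Cmax as a contrast from that model, and say which dose level's Cmax is meant. Keep the double-delta plot for display only. Another method that carries the placebo error, such as a patient-level bootstrap of the whole procedure, would also serve.

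State how serial correlation will be handled. At a 7-day residual correlation of 0.3, the one-step random-intercept model alone still rejected the slope in about 24% of null studies. In a further simulation of 500 runs per setting, adding patient-level robust variance brought slope rejection at that correlation from 25% to 5%.

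The cost is SAP wording and program code, with no new data. Intervals become wider: the one-step standard error is 1.6-2.4 times the SAP model's at Cmax and 1.4-1.5 times for the slope.

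A side note that carries no weight here: SAP 9.5.5 does not list the QTcF category summaries of Protocol 10.3.1.2. They may be in the TFL shells, which were not available.
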